**3.1.6 Intervention. a) Intervention group.** The goal of our breastfeeding intervention is consistent with AAP and ACOG guidelines: exclusive breastfeeding for the first 6 months of life, with continued breastfeeding as complementary foods are introduced through the infant's first year of life, or longer as mutually desired by the mother and her infant. Participant will complete 13 one-hour intervention visits: 5 during pregnancy and 8 in postpartum. Prenatal breastfeeding education will be weekly for 5 weeks at the PI's lab. After delivery, we will meet the participant at her home in 1 week, 2 weeks, and 1 month; and then monthly at the PI's lab until 6 months postpartum. Participants will receive \$15/visit compensation. Our team has rich experience in running behavioral interventions for the target population, for instance, most participants (73.9%) in the PI's smoking cessation study have completed 35 one-hour prenatal intervention visits and 12 monthly 1.5-hour postpartum follow-up visits with similar compensation (\$15/hour). The breastfeeding intervention components will include prenatal breastfeeding education, postnatal lactation counseling, family/peer/employer support, contingent financial incentives, and early limited formula milk via syringe (optional for at-risk infants).

**Component #1 - Prenatal breastfeeding education:** To maximize the effect, breastfeeding education will start in late pregnancy (28+ weeks) when the mother and family seriously plan on infant feeding. The breastfeeding plan will cover breastfeeding on demand, pain management, skin-to-skin contact, breastfeeding tips after cesarean section, lactation support, breastfeeding away from home, breast pump, maternity leave, and back-to-work scheduling. Educational approaches will include readings with quizzes (\$2 reward if passed), discussion, video, demonstration and practice with a baby simulator. Prenatal breastfeeding education will be delivered in a group with 6 pairs of participants and their family supporters per group. Physical examination of breasts and nipples will be conducted by a certified lactation counselor (CLC) to address potential issues including infectious conditions, dermatitis, breast masses, breast surgery, and flat or inverted nipples.

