**Table 1. Schedule for outcome and mediator measures**

| Measure                   | Pregnancy             | Postpartum (W-week, M-month) |    |    |    |    |    |    |                |                |
|---------------------------|-----------------------|------------------------------|----|----|----|----|----|----|----------------|----------------|
|                           | Enrollment (pre-test) | W1                           | W2 | M1 | M2 | M3 | M4 | M5 | M6 (post-test) | M9 (follow-up) |
| Outcomes           |                       |                              |    |    |    |    |    |    |                |                |
| Smoking status            | X                     | X                            | X  | X  | X  | X  | X  | X  | X              | X              |
| Breastfeeding (BF) status | BF intention          | X                            | X  | X  | X  | X  | X  | X  | X              | X              |
| Mediators          |                       |                              |    |    |    |    |    |    |                |                |
| Oxytocin and prolactin    |                       |                              |    | X  |    | X  |    | X  |                |                |
| Mother-infant bonding     |                       | X                            | X  | X  | X  | X  | X  | X  | X              | X              |
| Mother-infant interaction |                       |                              |    | X  |    | X  |    | X  |                |                |
| Maternal stress           | X                     | X                            | X  | X  | X  | X  | X  | X  | X              | X              |
| Maternal negative affect  | X                     | X                            | X  | X  | X  | X  | X  | X  | X              | X              |

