*Mother-infant bonding.* Mother-infant bonding will be measured with the Postpartum Bonding Questionnaire (PBQ) at all postpartum visits. PBQ is a 25-item scale reflecting a mother's feelings or attitudes towards her baby, such as "I feel close to my baby" and "I regret having this baby". Cronbach's alpha was 0.76 for the total PBQ scale, and test-retest reliability was 0.95, 0.95, 0.93, and 0.77 for the 4 subscales (impaired bonding, rejection and anger, anxiety about care, and risk of abuse), respectively. PBQ is a valid screening tool for bonding disorders and is well correlated with Kennerley Blues Scale.

*Mother-infant interaction.* At 1, 3, and 5 months postpartum, maternal and infant behaviors will be assessed during observations of mother-infant interactions during free play in the PI's lab. The observation room will be set up with toys on top of a colorful blanket placed on the floor. Mothers will be asked to spend some time with their infants as they normally would at home. These interactions will be videotaped for 10 minutes and independently coded by two coders blinded to group assignment or other information about mothers and infants. These observations will be coded using 5-point rating scales originally developed by Clark and used extensively in our prior studies led by [name] (Co-I). Three composite maternal scales will be derived: maternal sensitivity, negative affect, and positive engagement. Three composite infant behavior scales will be computed: infant responsiveness, positive affect, and negative affect. These scales are reliable and valid across different samples of substance using women, including pregnant smokers.

*Maternal stress.* We will measure maternal stress with Perceived Stress Scale (PSS) at enrollment and all postpartum visits. The 14-item PSS measures subjective stress or the degree to which life situations are appraised as stressful. Participants will report how often they have felt upset, nervous, angered, in control, or that they have coped effectively in the past month. Cronbach's alpha of PSS was 0.85 and test-retest reliability was 0.85. It was correlated with life-events, depressive and physical symptomatology, and social anxiety.

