*Maternal negative affect.* Maternal negative affect will be measured at enrollment and all postpartum visits using the Positive and Negative Affect Schedule (PANAS). The 10 items on negative affect include being distressed, upset, guilty, ashamed, hostile, irritable, nervous, jittery, scared, and afraid. Participants will rate their experience of each particular emotion in the past few weeks. With this time frame, its Cronbach's alpha was 0.87 and test-retest reliability was 0.48. In addition, we will measure maternal anxiety with the State-Trait Anxiety Inventory and postpartum depression with the Edinburgh Postnatal Depression Scale.

**3.1.10 Covariates.** We consider partner smoking, maternal secondhand smoke exposure, education, household income, health motivation, perceived social support, as covariates. They may confound our results and will be controlled in data analysis if not comparable between intervention and control groups.

**3.1.11 Economic costs.** We will collect information on intervention (not research and development) costs such as personnel, recruitment, materials, compensation, incentives, and transportation. We will include outcome costs for formula, medical care of NICU stay and sick child visits, and parental absenteeism for infant illness.

**3.1.12 Statistical Analysis.** *Specific Aim 1 (Breastfeeding promotion and postpartum smoking relapse).* The timing of postpartum smoking relapse (outcome) will be analyzed with Cox regression model by including group assignment (intervention vs control), smoking status (1=smoking, 0=non-smoking), the observed time, and significant covariates. The proportional hazard ratio of postpartum smoking relapse between two groups will be calculated. We will estimate Kaplan-Meier survival curves to visually compare smoking trajectories. Intent-to-treat analysis will be used with all randomized participants being included in their originally assigned groups. Dropouts, losses to follow-up, fetal deaths, and miscarriages will be coded as missing data on smoking status. If missing data on smoking status is more than 20%, we will run pattern mixture models and sensitivity analyses. A supplemental analysis will be run to examine *prenatal* smoking relapse during pregnancy.

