*Specific Aim 2 (Mediation analyses on mechanisms).* We will use dynamic path analysis to examine the mechanisms through which breastfeeding reduces smoking relapse. The dynamic path analysis includes simultaneous fitting of the Aalen additive hazards model (the R package 'timereg') and ordinary path analysis (PROC TCALIS in SAS). It fits our survival data with internal time-dependent mediators (e.g., oxytocin or prolactin) and a counting process as the outcome (i.e., smoking relapse). Hormonal baseline level and response to infant feeding (oxytocin or prolactin) will be included into the model as independent mediators. We will estimate the direct, indirect (through one or multiple mediators), and total effects of breastfeeding on smoking relapse (**Figure 1**). The PI has sufficient experience in mediation analysis.

**3.1.13 Sample size.** According to the literature, we estimate 45% rate of smoking relapse by 6 months postpartum in the control group. Assuming 45% protection effect of breastfeeding against postpartum smoking relapse, we estimate 25% (45%\*[1-45%]) rate of smoking relapse by 6 months postpartum in the intervention group. The corresponding sample size is 98 per group with type 1 error  $\alpha$  of 0.05 and power  $1-\beta$  of 0.8 to detect significant difference in smoking relapse between two groups in the larger R01 project. If 9-month postpartum smoking relapse rates (70% control vs 39% intervention) are used, the corresponding sample size is 46 per group. Therefore, 30 participants per group for this pilot study should provide sufficient sample size to test feasibility and efficacy as well as provide preliminary data regarding mediators and cost-effectiveness.

**3.2 Potential Problems & Alternative Strategies.** A potential challenge for the proposed project is to recruit a sufficient number of pregnant ex-smokers. If significant delay is observed, we will expand recruitment areas, use direct mailing, and advertise in local media. Another potential problem is attrition during intervention and follow-up periods. We expect 20% attrition rate due to dropouts, losses to follow-up, miscarriages, and fetal deaths. If we lose contact, we will reach out to the 3 people that have close relationship with the participant indicated at enrollment. We will recruit more participants to ensure sufficient statistical power if attrition is high.

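### The week 1 and week 2 stress and negative-affect scores partly recall pregnancy, so Aim 2 should start these mediator series at month 1 and adjust for the enrolment scores

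*Combined protocol and SAP*

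**What the plan says.** Section 3.1.9 sets the timing of the stress measure: "We will measure maternal stress with Perceived Stress Scale (PSS) at enrollment and all postpartum visits". Its recall period is the past month: "Participants will report how often they have felt upset, nervous, angered, in control, or that they have coped effectively in the past month". Negative affect is measured at the same visits with the PANAS, over a looser period: "Participants will rate their experience of each particular emotion in the past few weeks".

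Table 1 places both measures under Mediators and marks them at enrolment, W1, W2, M1 to M6 and M9. Section 3.1.6 fixes the early visits: "After delivery, we will meet the participant at her home in 1 week, 2 weeks, and 1 month".

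Section 3.1.12 (Specific Aim 2) uses dynamic path analysis "to examine the mechanisms through which breastfeeding reduces smoking relapse". Of the method it says "It fits our survival data with internal time-dependent mediators", naming the two hormones as examples. The estimands are set out as follows: "We will estimate the direct, indirect (through one or multiple mediators), and total effects of breastfeeding on smoking relapse".

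No section shortens the recall at W1 and W2, sets those scores aside, or says how they enter the model. The covariates in Section 3.1.10 do not include enrolment stress or affect, and those listed are adjusted for only if the arms differ on them.

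**The concern.** A mediator has to follow the exposure. The exposure in Aim 2 is breastfeeding, which starts after delivery, but a one-month recall taken one or two weeks after delivery reaches well back into pregnancy. Stress in late pregnancy may influence both whether a woman breastfeeds and whether she relapses. To that extent the early score carries a confounder as well as a mediator.

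Randomisation does not remove the problem, because breastfeeding itself is not randomised. Section 1 accepts that the direction of the association between breastfeeding and mood is hard to establish from observational data, so time order is part of what Aim 2 has to supply. Prenatal education also begins at 28 weeks or later. A difference between arms in the pregnancy part of the window could come from education or staff contact and be credited to breastfeeding.

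At stake is the early indirect effect through stress and affect, which is among the preliminary mediator data this pilot is meant to give the larger trial.

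**Working it through.** The plan gives no figure for this overlap, so there is none to reproduce. The check is a count of days.

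**Inputs**
- PSS recall window w: past month (Section 3.1.9). The documents give no day count; 28, 30 and 31 days are assumed.
- PANAS recall window w: past few weeks (Section 3.1.9). Again there is no day count; 14 to 28 days is assumed.
- Days since delivery d: 7 at W1, 14 at W2, about 30 at M1 (Section 3.1.6 and Table 1; no visit windows are stated).

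**Pregnancy share of the recall** = (w − d)/w, or 0 if d is at least w.

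| Scale and window | W1 (d = 7) | W2 (d = 14) | M1 (d = 30) |
|---|---|---|---|
| PSS, 28 days | 21/28 = 75% | 14/28 = 50% | 0% |
| PSS, 30 days | 23/30 = 77% | 16/30 = 53% | 0% |
| PSS, 31 days | 24/31 = 77% | 17/31 = 55% | 1/31 = 3% |
| PANAS, 14 days | 7/14 = 50% | 0% | 0% |
| PANAS, 21 days | 14/21 = 67% | 7/21 = 33% | 0% |
| PANAS, 28 days | 21/28 = 75% | 14/28 = 50% | 0% |

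**Sensitivity to recency.** If recent days weigh more, rising linearly from 0 for the oldest day to full weight today, the pregnancy share becomes ((w − d)/w)². For the PSS this gives 0.75² = 56% to (24/31)² = 60% at W1, and 0.50² = 25% to (17/31)² = 30% at W2. W1 stays mainly pregnancy; W2 becomes mainly postpartum.

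**Sensitivity to visit timing.** If the W2 visit falls on day 17, the PSS share is 11/28 = 39% to 14/31 = 45%.

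**How many scores are affected.** There are nine postpartum scores (W1, W2, M1 to M6, M9). Two are affected; seven remain from M1.

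**What a start at M1 gives up.** Section 3.1.13 assumes 45% relapse by 6 months in controls and 25% in the intervention group. With a constant hazard, relapse by month 1 is:
- controls: 1 − 0.55^(1/6) = 9.5%, or 0.095 × 30 ≈ 2.8 women;
- intervention: 1 − 0.75^(1/6) = 4.7%, or 0.047 × 30 ≈ 1.4 women.

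The constant hazard is only a convenience. Carried to 9 months it gives 1 − 0.55^1.5 = 59% in controls, against the plan's 70%.

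**The case against.** Three stronger readings are tempting, and the documents do not support them.

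- A reader might infer that the W1 and W2 scores cannot mediate at all, or that their use reverses the time order. They contain 7 and 14 postpartum days, and Section 3.1.6 aims for breastfeeding to start straight after delivery. The signal is diluted and mixed with prenatal stress, not absent.
- A reader might infer that both early stress scores mostly describe pregnancy. That fits W1. W2 is about half by day count, and less under recency weighting or a slightly late visit.
- A reader might infer that the affect scale fails in the same way at both visits. Its W2 share could be anywhere from 0% to 50%, because the recall period is not given in days.

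A tempting remedy is to treat the W1 and W2 scores as confounders and adjust for them. That would do harm. With a 30-day window, 7/30 = 23% of the W1 recall and 14/30 = 47% of the W2 recall follow birth, so adjustment would block part of the pathway Aim 2 is meant to estimate. For a relapse before the visit, the covariate would also be measured after the event.

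Two further objections carry weight. The plan names only the hormones as examples of time-dependent mediators and never says that every scheduled stress score enters the model, so use of the early scores is inferred from Table 1. And Aim 2 is exploratory, in a pilot of 30 per arm with few relapses expected before M1. Both limit the importance of the point. Neither settles how the early scores will be handled, and the analysis section is the place to say so.

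**Conclusion.** The point holds as a limited one about Aim 2. The W1 stress score is about three-quarters pregnancy by recall period and the W2 score about half; the affect score overlaps pregnancy at W1 and possibly at W2. Used as mediators of breastfeeding, these scores are mixed with prenatal stress, which may confound the path from breastfeeding through stress to relapse.

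The shares rest on an assumed month of 28 to 31 days, an assumed 14 to 28 days for the affect scale, visits on their nominal days and, in the main count, equal weight for each recalled day. The size of any resulting bias in the indirect effect cannot be worked out from the documents. Seven of nine postpartum scores, and the whole of Aim 1, are unaffected. It is a minor point, worth correcting because it costs little.

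**What to change.** Add to Section 3.1.12, Specific Aim 2:

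1. The enrolment PSS and PANAS scores are covariates in every mediator model and relapse model, whether or not the arms differ on them.
2. In the main analysis, the stress and negative-affect mediator series start at M1, where the hormone and mother-infant interaction measures also start.
3. The W1 and W2 scores enter as mediators only in a sensitivity analysis. They are not used as adjustment covariates, because they are partly post-exposure.

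The instruments, their recall wording and the visit schedule stay as they are, and the enrolment scores are already collected.

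There are two costs. First, the main analysis has no stress or affect mediator for relapses before M1: about 9.5% of controls under a constant hazard, and possibly more, since Section 3.1.6 (Component #4) treats the first month as a critical period for relapse. The sensitivity analysis recovers part of this. Second, the fix does not remove all prenatal confounding. Eligibility is at 28 weeks or earlier, so the enrolment score cannot capture stress in the last weeks of pregnancy. The report should state that limit.

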controlled trial to assess the effect of breastfeeding promotion on postpartum smoking relapse. It can help to yield causal evidence by overcoming self-selection bias and confounding (e.g., health motivation, socio-economic status [SES], partner and family support) in previous observational research. Secondly, we will collect pilot data to examine neuroendocrine (oxytocin and prolactin), behavioral (mother-infant interaction), and psychological (mother-infant bonding, stress, and negative affect) mechanisms through which breastfeeding may reduce risk of postpartum smoking relapse. Thirdly, this is a pioneering study to combine contingent incentives with other intervention strategies such as education, counseling, support, and early limited formula milk via syringe to further improve breastfeeding practice among disadvantaged mothers.

[figure not shown]

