**Figure 1. Conceptual Model for Breastfeeding and Smoking Abstinence\***

\* Other hormonal mechanisms, such as progesterone, estrogen, ACTH, cortisol, and tetraiodothyronine (T4), will be included in the larger R01 grant.

must be at 28 weeks of pregnancy or earlier to ensure adequate time for prenatal breastfeeding intervention. Exclusion criteria are teen pregnancy (<18 y); current use of other tobacco or nicotine products; medical conditions contraindicating breastfeeding such as HIV infection, active tuberculosis, and breast removal; current heavy drinking (more than 2 drinks a day); current use of other psychoactive substances; being strongly against breastfeeding; and non-English speakers. To increase the possibility to obtain a representative sample of the generable population, the study will be advertised as a program to promote healthy infant feeding among pregnant women without requiring breastfeeding intention or mentioning smoking relapse prevention. We will not exclude women without current intention to breastfeed (28.6% in our pilot survey), unless they are strongly against breastfeeding (4.8%). Similarly, we will not exclude women who plan to relapse after delivery (0% in our pilot survey), as our breastfeeding promotion may motivate them to maintain abstinent for a longer period especially if they know tobacco metabolites are concentrated in breast milk.

**3.1.4 Pre-test visit.** During this visit, we will measure the participant's urine cotinine, height, and body weight. Participants will complete a survey on smoking temptations, nicotine dependence before quitting, smoking cessation history, self-efficacy to maintain smoking abstinence, smoking environment including partner smoking behaviors, breast health, breastfeeding knowledge, breastfeeding history, relationship with partner and other family members, social network, stress, negative affect, physical activity, sleep, and diet.

**3.1.5 Randomization.** At 28 weeks of pregnancy, eligible participants will be randomized into either the intervention group (N=30) or the control group (N=30) using a sequence of random numbers in blocks of 2, which can ensure equal or close numbers of participants between the two groups throughout the project.

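### The only covariate rule available to Aim 2 is triggered by imbalance between randomised arms, so it leaves the non-randomised mediation paths open to confounding

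*Combined protocol and SAP*

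**What the plan says.** Section 3.1.10 sets the candidate covariates: "We consider partner smoking, maternal secondhand smoke exposure, education, household income, health motivation", with perceived social support as the sixth. The trigger follows: "They may confound our results and will be controlled in data analysis if not comparable between intervention and control groups". No threshold for comparability is given.

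Section 3.1.12 mentions covariates once more, as those found significant, but only within the Aim 1 Cox model. For Aim 2 it plans a dynamic path analysis that combines an Aalen additive hazards model with ordinary path analysis: "We will estimate the direct, indirect (through one or multiple mediators), and total effects of breastfeeding on smoking relapse". The Aim 2 text names no covariate, no confounding assumption and no sensitivity analysis.

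Stress and negative affect have pre-randomisation values. Section 3.1.9 states: "We will measure maternal stress with Perceived Stress Scale (PSS) at enrollment and all postpartum visits". It also states: "Maternal negative affect will be measured at enrollment and all postpartum visits using the Positive and Negative Affect Schedule (PANAS"). The pre-test survey in 3.1.4 covers "relationship with partner and other family members, social network, stress, negative affect, physical activity, sleep, and diet". Neither stress nor negative affect is on the 3.1.10 list; in the analysis they appear only as mediators.

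The plan names likely confounders itself. Section 2 says that randomisation overcomes self-selection and confounding ("e.g., health motivation, socio-economic status [SES], partner and family support) in previous observational research"). Section 1 calls stress and negative affect common relapse triggers, and says that the direction of their association with breastfeeding is hard to establish from observational data.

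**The concern.** Breastfeeding and every mediator in Table 1 arise after randomisation. A baseline factor can be perfectly balanced between arms and still differ between women who breastfeed and women who do not, or between women with high and low postpartum stress. A rule that looks only at arm balance therefore tests the wrong comparison for Aim 2. When the arms are balanced, it leaves out the very factors that section 2 names. It can never bring in enrolment stress or negative affect, because they are not listed.

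At stake is the mechanism evidence that the pilot is meant to carry into the R01 application. Self-selection could be read as a direct or mediated effect of breastfeeding.

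**Working it through.** **Which paths are protected.** The plan uses the word breastfeeding in two ways. In Aim 2 it is the exposure. In 3.1.13 an effect of breastfeeding ("Assuming 45% protection effect of breastfeeding against postpartum smoking relapse") is applied to the contrast between intervention and control. The two readings give:

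| Path | Exposure = assigned arm | Exposure = actual feeding |
|---|---|---|
| Exposure to relapse (total) | randomised | open to confounding |
| Exposure to mediator | randomised | open to confounding |
| Mediator to relapse | open to confounding | open to confounding |

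The mediator-to-relapse path is unprotected under both readings. Any indirect effect, and the direct effect estimated alongside it, depends on that path.

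**How often the rule would act.** Under randomisation, a between-arm test at level *a* flags a baseline covariate with probability about *a*, however strongly it confounds Aim 2.

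**Size, exposure = actual feeding.** All inputs are assumed: no true effect; one binary confounder with 50% prevalence, exactly balanced by arm; odds ratio 2 or 3 against breastfeeding; relapse risk ratio R of 1.5 to 3. Breastfeeding rates are 72% vs 0% (the earlier-study 6-month figures in section 1, as illustration only) or an assumed 60% vs 20%. With confounder prevalence pB in breastfeeders and pN in the others:

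spurious RR = (1 + pB(R − 1)) / (1 + pN(R − 1))

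| Rates | Odds ratio | pB | pN | R = 1.5 | R = 2 | R = 3 |
|---|---|---|---|---|---|---|
| 72/0 | 2 | 0.452 | 0.527 | 0.970 | 0.951 | 0.927 |
| 72/0 | 3 | 0.426 | 0.542 | 0.955 | 0.925 | 0.889 |
| 60/20 | 2 | 0.415 | 0.557 | 0.944 | 0.909 | 0.865 |
| 60/20 | 3 | 0.368 | 0.588 | 0.915 | 0.861 | 0.797 |

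**Size, exposure = assigned arm.** The reference is the additive hazard difference implied by 45% vs 25% at 6 months: −ln(0.55)/6 + ln(0.75)/6 = 0.0517 per month. In simulation with a null stress mediator and comparable assumed confounders, the total effect stayed within 0.0002 of zero. The spurious indirect effect was 1.0% to 7.3% of the reference.

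**Leaving out enrolment stress.** Assumed: correlation 0.5 to 0.7 with postpartum stress, direct relapse hazard ratio 1.2 to 1.5 per SD, and the binary confounder already adjusted. The spurious indirect effect was 7% to 22% of the reference with actual feeding as exposure, and 3% to 15% with arm as exposure.

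**Rule against fixed adjustment.** A separate Cox simulation used 60 women, no true effects, and a continuous baseline factor acting on breastfeeding, mediator and relapse with coefficients from 0.3 up to 0.8. The rule was taken as p < 0.05 and flagged the factor about 4% of the time. Median hazard ratios:

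| | Breastfeeding | Mediator |
|---|---|---|
| No adjustment | 0.98, 0.96, 0.84 | 0.92, 0.83, 0.78 |
| 3.1.10 rule | 0.98, 0.96, 0.85 | 0.92, 0.83, 0.79 |
| Always adjusted | 1.00, 1.00, 1.02 | about 1.00 |

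At n = 2000 in the middle setting the rule still gave 0.95 and 0.83.

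**Bias against noise, horizons matched.** SE(log HR) = 2/√events. On the log scale, 0.889 is 0.118 and 0.797 is 0.227.

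| Horizon | Per group | Events | SE | 0.889 | 0.797 |
|---|---|---|---|---|---|
| 6 months | 30 | 30(0.45 + 0.25) = 21 | 0.436 | 0.27 SE | 0.52 SE |
| 6 months | 98 | 98(0.45 + 0.25) = 68.6 | 0.241 | 0.49 SE | 0.94 SE |
| 9 months | 30 | 30(0.70 + 0.39) = 32.7 | 0.350 | 0.34 SE | 0.65 SE |
| 9 months | 98 | 98(0.70 + 0.39) = 106.8 | 0.194 | 0.61 SE | 1.17 SE |

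The bias is constant, so its share of the standard error grows with the sample.

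**The case against.** **The exposure may be the assigned arm.** Section 3.1.13 points that way, and Figure 1, which Aim 2 cites, is not shown. A reader might infer that the breastfeeding-to-relapse effect is confounded whatever the plan means. The text does not support that: under the arm reading the total effect is randomised. The mediator-to-relapse path remains exposed.

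**The rule may act more often than 4%.** Comparability is undefined. With 30 per arm, a standardised difference has SE √(2/30) = 0.258, so a threshold of 0.1 would flag a listed covariate about 70% of the time and 0.25 about 33%. Exact balance is therefore the unfavourable case for the rule. This stands, but adjustment would still enter by chance, and never for the unlisted stress and affect values.

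**The enrolment-stress figures are fragile.** They need enrolment stress to affect relapse other than through later stress. The plan also gives a test-retest reliability of 0.48 for PANAS over the time frame used, so correlations of 0.5 to 0.7 may not carry over to negative affect. This stands, and those percentages are illustrations only.

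**A long adjustment list can do harm.** This also stands. In simulation at 30 per arm and 72/0 rates, a seven-term model with both group and breastfeeding raised the root mean squared error of the breastfeeding coefficient from about 0.035–0.039 to 0.066–0.077 per month, because the two are strongly collinear.

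**Aim 2 is pilot work.** That limits the severity, but does not make an arm-imbalance rule suitable for these paths.

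**Conclusion.** The concern holds for Aim 2. Followed as written, the plan would control confounding of the mediator-to-relapse path only by accident, and confounding of the breastfeeding paths as well if the exposure is actual feeding. This is an unsuitable rule, not merely missing detail, because 3.1.10 is the only rule that reaches Aim 2.

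The size cannot be established from the documents. The figures above rest on assumed confounder strengths and show only that the bias is plausible, modest against pilot noise, and persistent at the planned R01 size.

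Two stronger inferences should be resisted. Aim 1 is not biased: its group contrast is randomised and valid unadjusted. Nor do the documents show that Aim 2's results will be materially wrong, since they give no confounder effects.

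**What to change.** A cheap improvement, confined to analysis text:

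- In 3.1.12, state whether the Aim 2 exposure is assigned group or actual feeding.
- For Aim 2, replace the imbalance trigger with a very short fixed set of baseline values, used regardless of arm balance: the enrolment PSS or PANAS value when stress or negative affect is the mediator, plus one or two prespecified confounders such as partner smoking and one SES measure (income or education).
- Do not by default put group and actual breastfeeding together in the main hazard model. Report the randomised group effect separately.
- Keep the planned single- and multiple-mediator models. State that bonding, interaction and hormones have no enrolment value in Table 1, so this adjustment is unavailable for them.
- Label all non-randomised paths observational and exploratory.

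No new data collection is needed. In simulation at 30 per arm, adding only the enrolment mediator value and one confounder left the breastfeeding root mean squared error about unchanged (0.037–0.040). It removed the mediator-coefficient bias (about 0.02 to about 0) and cut the mediator error from 0.025–0.027 to 0.020–0.023. At 98 per group the mediator error fell by roughly half. These gains assume that the confounders are perfectly measured and are the only ones.

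The cost is slightly wider intervals. Exposure, one mediator, its enrolment value and two confounders make five terms, so 21/5 = 4.2 to 32.7/5 = 6.5 events per term. Unmeasured confounding remains.
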